10.9 Concomitant Medications

Concomitant medications will be summarized in tables, by study arm and overall for each of the three cohorts, and by study arm and overall for the three cohorts combined. These tables will summarize:

- Number and percentage of randomized participants who had any concomitant medications (yes or no), and the number of medications.
- Number and percentage of randomized participants with at least one concomitant medication in each observed ATC Level 3 category, and the total number of concomitant medications in each ATC Level 3 category.
- Within each ATC Level 3 category, the number and percentage of randomized participants with at least one concomitant medication in each observed ATC Level 1 category, and the total number of concomitant medications in each ATC Level 1 category. The denominator for these percentages is the number of participants in the ITT Analysis Set.

Concomitant medications are defined as medications recorded on the Concomitant Medications Log CRF that overlapped with a participants' time on study; i.e., that had a "Date stopped" on or after the participant's randomization date, or that were marked "Ongoing".

10.10 Infant Concomitant Medications

Infant concomitant medications will be summarized in tables, by study arm and overall for each of the three cohorts, and by study arm and overall for the three cohorts combined.

- Number and percentage of enrolled infants who had any concomitant medications (yes or no), and the number of medications.
- Number and percentage of enrolled infants with at least one concomitant medication in each observed ATC Level 3 category, and the total number of concomitant medications in each ATC Level 3 category.
- Within each ATC Level 3 category, the number and percentage of enrolled infants with at least one concomitant medication in each observed ATC Level 1 category, and the total number of concomitant medications in each ATC Level 1 category. The denominator for these percentages is the number of infants in the ITT Analysis Set.

Infant concomitant medications are defined as medications recorded on the Concomitant Medications Log CRF that overlapped with an infant's time on study; i.e., that had a "Date stopped" on or after the infant's birth date, or that were marked "Ongoing".

10.11 Physical Examination

Tables summarizing physical examination findings will be prepared. These summaries will be by visit, by arm and overall for each of the three cohorts, and by visit, by arm and overall for the three cohorts combined. These will be summarized for visits where the physical examination was expected to be performed.

Expected visits for physical examinations are the following:

- Screening (visit 1)
- 4-week visits (e.g., visit 6, visit 10, visit 14, etc.; these visits only for Cohorts 2 and 3) (targeted exam only, i.e., only general appearance)
- PPO visit (visit 101) (targeted exam only, i.e., only general appearance)

These tables will use data collected on the Physical Examination CRF and will include:

- Number and percentage of participants with a physical exam (non-missing value on the “Physical exam” item), with the denominator being the number of participants in the ITT Analysis Set who completed the visit.
- Number and percentage of participants with each physical exam result (not done, normal, or abnormal findings), with the denominator being the number with a physical exam. Note that a result being missing entirely is treated as different from a result being marked as “not done”
 - The “General appearance” item will be summarized for all expected visits. The remaining items will only be summarized for Screening.

10.12 Infant Physical Exam

Tables summarizing infant physical examination findings will be prepared. These summaries will be by visit, by arm and overall for each of the three cohorts, and by visit, by arm and overall for the three cohorts combined. These will be summarized for visits where the infant physical examination was expected to be performed.

Expected visits for physical examinations are the following:

- PPO visit (visit 201)
- 6-week PPO visit (visit 203)
- 6-month PPO visit (visit 204)
- 12-month PPO visit/early SEV (visit 205)

These tables will use data collected on the Physical Examination CRF and will include:

- Number and percentage of infants with a physical exam (non-missing value on the “Physical exam” item), with the denominator being the number of infants in the ITT Analysis Set who completed the visit.
- Number and percentage of infants with each physical exam result (not done, normal, or abnormal findings), with the denominator being the number with a physical exam. Note that a result being missing entirely is treated as different from a result being marked as “not done”
 - The “Heart/Cardiovascular”, “Lung/Respiratory”, and “General appearance” items will be summarized for all expected visits. The remaining items will only be summarized for the PPO visit.

10.13 Infant Ages and Stages Assessment

Tables summarizing infant ages and stages will be prepared. These summaries will be by visit, by arm and overall for each of the three cohorts, and by visit, by arm and overall for the three cohorts combined. These will be summarized for visits where the infant ages and stages assessment was expected to be collected, which are the 6-month PPO visit (visit 204) and the 12-month PPO visit/early SEV (visit 205).

These tables will use data collected on the Infant Ages and Stages Assessment CRF and will include:

Number and percentage of infants with an Ages and Stages Assessment completed (non-missing value on the “Was the Ages and Stages Assessment Completed?” item), with the denominator being the number of infants in the ITT Analysis Set who completed the visit.

Summaries of the “Communication total”, “Gross Motor total”, “Fine Motor total”, “Problem solving total”, and “Personal-Social total” items as continuous variables.

Number and percentage of infants with abnormalities observed for communication, gross motor,

- fine motor, problem solving, personal-social, and other abnormalities, with the denominator being the number of infants with the Ages and Stages Assessment completed.
- Summary of the sum of the communication, gross motor, fine motor, problem solving, and person-social totals, as a continuous variable.
- Number and percentage of infants with any abnormality observed (across communication, gross motor, fine motor, problem solving, personal-social, and other), and the total number of abnormalities.

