7.6 Pelvic Exam

Baseline pelvic examination findings will be summarized in tables, by study arm and overall for each of the three cohorts, and by study arm and overall for the three cohorts combined. These tables will use data collected on the Pelvic Exam CRF at the enrollment visit and will include:

- Number and percentage of participants with a pelvic exam assessment (non-missing value on the “Pelvic exam assessment” item), with the denominator being the number of participants in the ITT Analysis Set.
- Number and percentage of participants with each pelvic exam assessment result (not done, abnormal findings, or no abnormal findings), with the denominator being the number with a non-missing pelvic exam assessment result. Note that a result being missing entirely is treated as different from a result being marked as “not done”.
- Number and percentage of participants with each type of abnormal pelvic exam finding (from vulvar edema through other abnormal findings), with the denominator being the number with a non-missing pelvic exam assessment result.
 - For the abnormal vaginal discharge finding, the number and percentage of participants who had each type of abnormal vaginal discharge (slight, moderate, or pooling) will also be summarized, with the denominator being the number of participants with an abnormal vaginal discharge finding.

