10.14 Edinburgh Postnatal Depression Scale

Tables summarizing results from the Edinburgh Postnatal Depression Scale will be prepared. These summaries will be by visit, by arm and overall for each of the three cohorts, and by visit, by arm and overall for the three cohorts combined. These will be summarized for visits where the questionnaire was expected to be administered.

Expected visits for the Edinburgh Postnatal Depression Scale are the following:

- Enrollment visit (visit 2)
- 4-week visit corresponding to, or immediately following, the 30th week of gestation (only for Cohort 3; this is visit 6 if the gestational age at enrollment was 26-29 weeks, visit 10 if the GA was 22-25 weeks, visit 14 if the GA was 18-21 weeks, visit 18 if the GA was 14-17 weeks, or visit 22 if the GA was 12-13 weeks)
- 6-week PPO visit (visit 103)

These tables will use data collected on the Edinburgh Postnatal Depression Score CRF and will include:

- Number and percentage of participants with an assessment performed (“Was this assessment performed?” was “Yes”), with the denominator being the number of participants in the ITT Analysis Set who completed the visit.
- Number and percentage of participants with each response to the 10 items on the questionnaire (“I have been able to laugh and see the funny side of things”, “I have looked forward with enjoyment to things”, “I have blamed myself unnecessarily when things went wrong”, “I have been anxious or worried for no good reason”, “I have felt scared or panicky for no very good reason”, “Things have been getting on top of me”, “I have been so unhappy that I have had difficulty sleeping”, “I have felt sad or miserable”, “I have been so unhappy that I have been crying”, “The thought of harming myself has occurred to me”), with the denominator being the number of participants in the ITT Analysis Set with an assessment performed.
- Number and percentage of participants who were subsequently referred for further evaluation and/or management (“Following completion of this questionnaire, was the mother subsequently referred for further evaluation and/or management”), with the denominator being the number of participants in the ITT Analysis Set with an assessment performed.
- Summary of the EPDS Score as a continuous variable.

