10.16 Social Benefits

Tables summarizing social benefits will be prepared and will be by arm and overall for each of the three cohorts, and by arm and overall for the three cohorts combined. These summaries will include responses from the Social Benefits CRF collected at the 6-week PPO visit (visit 103), including interim 6-week PPO visits for participants who did not have the Social Benefits CRF collected at their scheduled 6-week PPO visit.

These tables will include:

- Numbers and percentages of participants with each possible response to items under “From your perspective, what are all the benefits of participating in this study?” (i.e., from “The financial reimbursement”, “Free health care from the study”,..., “To help my relationship with my partner and/or family”, and “Other”), with the denominators being the number of participants in the ITT Analysis Set.
- Number and percentage of participants with each response to “What is the most important benefit or reason for your participation in this study?”, with the denominator being the number of participants in the ITT Analysis Set.

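### SAP 10.13 counts an Ages and Stages Assessment as completed on any non-missing answer, so a recorded 'No' inflates the completion count and dilutes the domain-level abnormality percentages

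*SAP*

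**What the plan says.** Section 10.13 summarises the infant Ages and Stages Assessment at the 6-month and 12-month visits, by arm and overall. Four statements matter here.

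- The first line of the table is "Number and percentage of infants with an Ages and Stages Assessment completed (non-missing value on the" item worded "Was the Ages and Stages Assessment Completed". Its denominator is the infants in the ITT set who completed the visit.
- The percentages with an abnormality in each domain (and for other abnormalities) are taken "with the denominator being the number of infants with the Ages and Stages Assessment completed".
- A later line gives "Number and percentage of infants with any abnormality observed (across communication, gross motor" and the remaining domains). It states no denominator.
- Domain totals and their sum are summarised as continuous variables.

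Two other sections treat the same situation differently. Section 10.14, on the Edinburgh scale, gives the "Number and percentage of participants with an assessment performed" and counts an assessment only if the corresponding item was answered *Yes*. Section 10.8 takes a woman out of the denominator for trichomonas, gonorrhea or chlamydia when the sample was not collected or the test was not done or is missing.

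**The concern.** The item asks whether the assessment took place. Whether that item was answered and whether the assessment was completed are two different things, and 10.13 uses the first to define the second. If the rule is programmed as written, a form marked *No* adds one infant to the completed count and one to the denominator of the domain percentages, but can never add to a numerator. The error can therefore only lower the domain abnormality percentages.

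The trial is descriptive, so the printed percentage is what readers will use, and this table is part of the infant safety reporting. The lines specified for 10.13 include no row for assessments not done, so a reader could not detect or undo the dilution from the table alone.

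**Working it through.** **Inputs.** The SAP states no abnormality rate, no completion rate and no share of *No* answers for this assessment, so there is no figure of its own to reproduce. The values of p and q below are assumptions. N = 400 is the planned number of mothers in the ring arm (SAP Table 1), used as a stand-in for infants. As a check on the interval method, exact binomial limits return the SAP's Table 2 entries: an upper bound of 0.92% for 0/400, and 0.03% to 5.45% for 1/100.

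**Formulas.** Let M be the number of infants with a non-missing answer, q the share of those answers that are *No*, and p the abnormality rate among infants actually assessed.

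- Assessed infants: M(1 − q). Infants with an abnormality: pM(1 − q).
- Rate under 10.13 as written: pM(1 − q) / M = p(1 − q).
- Rate if completed means *Yes*: pM(1 − q) / [M(1 − q)] = p.
- Completed count as written: M, against M(1 − q) under *Yes*, so it is overstated by a factor of 1/(1 − q).

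**Results (p and q assumed).**

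| q | p = 10%, as written | p = 5%, as written |
|---|---|---|
| 0% | 10.0% | 5.0% |
| 5% | 9.5% | 4.75% |
| 10% | 9.0% | 4.5% |
| 20% | 8.0% | 4.0% |

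A *Yes* rule prints 10.0% and 5.0% in every row.

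**One worked case.** Take M = 400, q = 10%, p = 10%. Assessed: 400 × 0.90 = 360. With an abnormality: 0.10 × 360 = 36.

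- As written: 36/400 = 9.0% (95% exact interval 6.38 to 12.24).
- Under *Yes*: 36/360 = 10.0% (7.10 to 13.57).
- Completion, if the item is answered for all 400 infants at the visit: 400/400 = 100% as written, against 360/400 = 90%.

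**Unequal q by arm.** If q were 5% in one arm and 20% in the other, equal rates of 10% would print as 0.10 × 0.95 = 9.5% and 0.10 × 0.80 = 8.0%. Nothing in the SAP suggests such a split. It only shows how the rule would behave.

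**What is not touched.** An unassessed infant has no domain scores, so the continuous summaries are not diluted. Counts of abnormalities are also unchanged. The primary infant safety endpoint in 8.2 has its own denominator.

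**The case against.** The strongest reply is that the size is unknown and may be zero. The case report form is not shown, so *No* as a response option is inferred from the wording of the item and from the parallel item in 10.14. If sites left the form blank or did not file it for unassessed infants, those infants are missing and the rule does no harm. Even at q = 10% the shift from 10.0% to 9.0% lies well inside either exact interval. The assessment is neither a primary nor a listed secondary endpoint, and no test or decision hangs on it. All of this stands, and it limits the consequence. It does not make the definition right.

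A reader might also infer several stronger claims, which the SAP does not support.

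- *The same error runs through the other tables.* In 10.11 and 10.12 results are given "with the denominator being the number with a physical exam", and that count does include exams marked not done. But not done is a printed category of its own, and the SAP deliberately separates it from missing, so non-assessment is visible and the reader can rebase. Section 7.6 also prints a not-done row. Its abnormal-finding percentages, taken "with the denominator being the number with a non-missing pelvic exam assessment result", do include exams not done, but this is a baseline table and the reader can correct it.
- *Social benefits in 10.16 is another instance.* It is a separate matter. There is no completion item to misread, only an explicit choice of percentages "with the denominators being the number of participants in the ITT Analysis Set" for perceived benefits of taking part. It does not belong to this point.
- *Every abnormality percentage is diluted.* The stated denominator attaches to the domain-level line. The any-abnormality line has none, which is a gap to fill rather than a demonstrated bias.
- *The completion rate will print near 100% whatever happens.* Infants who completed the visit but have a blank item or no form still lower it. It reaches 100% only if the item is answered for every infant at the visit.

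**Conclusion.** The point holds for 10.13. The definition as written gives a wrong completed count, and domain-level abnormality percentages that are too low, whenever a *No* is recorded. The relative dilution equals q. Under assumed values, a 10% rate prints as 9.5%, 9.0% or 8.0% for q of 5%, 10% or 20%, and there is no effect at q = 0. The conclusion rests on the literal wording of 10.13 and on *No* being a recordable answer. The magnitudes rest on assumed p and q, because the SAP gives neither.

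This should be corrected because it concerns an infant safety table and the correction costs almost nothing. It does not call the primary endpoints or the continuous developmental scores into question. The pelvic findings in 7.6 are a minor consistency point.

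**What to change.** - **10.13, completion:** define a completed assessment as the item answered *Yes*, as 10.14 does for its own item. Keep the infants who completed the visit as the denominator of the completion percentage.
- **10.13, abnormalities:** use the *Yes* count as the denominator for the domain-level percentages, and state the same denominator for the any-abnormality line.
- **7.6 (minor):** base the abnormal pelvic finding percentages on exams actually done, and keep the existing not-done row.

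No change is needed in 10.11 or 10.12 on this account. The cost is a few words in the SAP and the matching table specifications, with no new data. If no *No* was recorded in 10.13 and no pelvic exam was marked not done, every stated percentage stays the same. Otherwise the abnormality percentages rise and the developmental completion percentage falls to its proper value.

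### Section 10.13 counts an Ages and Stages assessment as completed on any non-missing answer, so a recorded No would enter the denominator of the infant developmental abnormality percentages

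*SAP*

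**What the plan says.** Section 10.13 plans tables at the 6-month and 12-month visits. The first row is the number and percentage of "infants with an Ages and Stages Assessment completed (non-missing value on the" item asking whether the assessment was completed, out of ITT infants who completed the visit. A later bullet gives the percentages with an abnormality in communication, gross motor, fine motor, problem solving, personal-social and other, "with the denominator being the number of infants with the Ages and Stages Assessment completed". The domain totals and their sum are summarised as continuous variables. A final bullet on any abnormality states no denominator.

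Section 10.14, for the Edinburgh scale, counts participants with an "assessment performed (“Was this assessment performed?” was “Yes", and uses that count as the denominator for the item responses and referrals.

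Three examination sections use non-missing rules too:

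- Section 7.6 (baseline pelvic exam) has three result levels, one of which is 'not done'. It divides each type of abnormal finding by all non-missing results, and adds: "Note that a result being missing entirely is treated as different from a result being marked as" not done.
- Section 10.11 (maternal physical exam) has "Number and percentage of participants with a physical exam (non-missing value on the" exam item, then "each physical exam result (not done, normal, or abnormal findings), with the denominator being the number with a physical exam".
- Section 10.12 (infant physical exam) uses the same structure: "Number and percentage of infants with each physical exam result (not done, normal, or abnormal findings").

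**The concern.** A non-missing answer to a yes/no gate question shows that the question was answered. It does not show that the assessment took place. If 10.13 is programmed as written, an infant recorded as not assessed is counted as assessed.

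That infant cannot contribute an abnormality to the numerator but does enter the denominator, so the bias in the affected percentages runs one way, towards fewer abnormalities. The completion row rises at the same time, and since 10.13 plans no row for No, a reader of the table could see neither effect.

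These are the planned neurodevelopmental results for the infants. The study's primary objectives include describing infant safety, and section 3.2 makes the analyses descriptive unless otherwise noted. The printed percentage is therefore itself the result, with no later modelling step at which the error might be noticed.

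**Working it through.** **Rules side by side**

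| SAP section | Counted as done when | Is a negative answer shown on its own row? |
|---|---|---|
| 10.13 Ages and Stages | item is non-missing | no |
| 10.14 Edinburgh scale | item is Yes | not needed; No is excluded from the denominator |
| 7.6 Pelvic exam | result is non-missing, with 'not done' one of its levels | yes |
| 10.11, 10.12 Physical exam | exam item is non-missing; 'not done' listed among the results | yes |

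Sections 10.13 and 10.14 treat equivalent gate items differently, and no reason is given.

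**Inputs.** The SAP states no completion or abnormality rate for these tables, so there is no figure of its own to reproduce. Let:

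- n = infants who completed the visit
- f = those with a non-missing answer to the item
- x = share of those f answers that are No
- p = true abnormality proportion among infants actually assessed

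The values of x and p below are assumptions.

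**Completion**

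- As written: f/n.
- Counting Yes only: f(1 − x)/n.
- Overstatement: x·f/n, which equals x when every infant at the visit has a form (f = n).

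**Abnormality percentage**

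- Infants with an abnormality: p·f(1 − x).
- As written: p·f(1 − x)/f = p(1 − x).
- Counting Yes only: p.
- The printed percentage is the true one times (1 − x), whatever f/n is.

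**Numbers, with f = n**

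| x (assumed) | Completion as written | Completion, Yes only | True 10% prints as | True 5% prints as |
|---|---|---|---|---|
| 0% | 100% | 100% | 10.0% | 5.0% |
| 2% | 100% | 98% | 9.8% | 4.9% |
| 5% | 100% | 95% | 9.5% | 4.75% |
| 10% | 100% | 90% | 9.0% | 4.5% |
| 20% | 100% | 80% | 8.0% | 4.0% |

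Worked case: take 400 infants, borrowing the planned ring-arm size only as a convenient number, and x = 5%. Then 20 were not assessed and 380 were. A true 10% is 38 infants, and 38/400 = 9.5%.

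If x differed by arm, equal true rates would print unequally. At the extremes of this range, a true 10% in both arms would show as 9.8% and 8.0%.

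**What is not affected.** An infant who was not assessed has no scores, so the domain totals and their sum should not change. For the any-abnormality bullet the effect cannot be worked out, because no denominator is stated.

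**Section 7.6.** The same factor applies to each type of pelvic finding, with x now the share of non-missing results marked 'not done'. Here that share is printed in the table.

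**The case against.** The best defence is that this is a wording slip with little practical reach. The case-report form is not shown, so the No option is inferred from how the item is phrased. The completion row is already limited to infants who completed the visit, so x covers only those who attended without being assessed. An infant whose form was left blank or never filed is correctly counted as not completed. A completion rate printing near 100% therefore needs a form marked No for nearly every unassessed infant. All of this stands, and it limits the size. It does not make the 10.13 rule right, nor explain why 10.14 differs.

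A reader might infer that the examination sections share the fault in full, with missed exams hidden and unexamined infants or mothers counted as normal. The SAP does not support that. Sections 7.6, 10.11 and 10.12 each list 'not done' as its own result and separate it from missing, so the count is visible and a reader can recompute any percentage. In 10.11 and 10.12 the sub-bullets refer to individual items such as general appearance. 'Not done' may therefore describe one item within an exam that did take place, in which case the denominator is reasonable. Only in 7.6 is 'not done' plainly inside the denominator for abnormal findings, and that is a baseline table.

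A reader might also infer that the primary infant safety result is diluted. It is not: sections 8.1 and 8.2 count serious and Grade 3 or higher adverse events and do not use these denominators.

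**Conclusion.** The rule in 10.13 is wrong as written. It counts a recorded No as a completed assessment, uses that count as the denominator for the domain and 'other' abnormality percentages, and disagrees with 10.14.

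The relative reduction in those percentages equals x, the share of filed forms that say No. Over the assumed range of 2% to 20% the distortion is modest, and it is nil if no form says No. The conclusion rests on the item accepting No as an answer, which its wording implies but the SAP does not show.

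The defect is worth correcting because the affected tables give no sign of it. The point in 7.6 is secondary, and in 10.11 and 10.12 the text is ambiguous rather than shown to be wrong.

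**What to change.** **Section 10.13.** Define completed as the gate item being Yes, as 10.14 does. Use that count as the denominator for all abnormality percentages, and state it for the any-abnormality bullet as well. A row giving the number of No answers would make the shortfall visible.

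**Section 7.6.** Divide each abnormal pelvic finding by exams actually done, meaning results of abnormal or no abnormal findings. Keep the existing 'not done' row.

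**Sections 10.11 and 10.12.** State that an exam marked 'not done' as a whole is not counted as a participant or infant with a physical exam. Say whether 'not done' in the result rows refers to the whole exam or to a single item.

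**Cost.** A few wording changes and denominator flags in the table programs, with no new data. Reported completion may fall slightly and some abnormality percentages may rise slightly.
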